#### 1.4 Clinical Data to Date

Solid back and cluster hole versions of the Tritanium® Acetabular Shell are currently available in the United States. This study is the first prospective data collection on both versions of the device.

### 2 Study Objectives

#### 2.1 Efficacy

#### 2.1.1 Primary

The primary objective of this study will be to evaluate the success rate of cementless primary THR in hips implanted with the Tritanium® Acetabular Shell, as compared to the published results of similar acetabular components. Success will be defined as absence of acetabular shell revision for any reason at 5 years postoperative. It is expected that the survivorship of the Tritanium® Acetabular Shell group will be non-inferior to the survivorship reported in the literature for similar competitive devices.

#### 2.1.2 Secondary

Usage of bone screw fixation will be recorded and compared between the Tritanium® Acetabular Shell group and the Trident® HA Hemispherical Shell group (Trident® X3® Polyethylene Insert Study).

Additionally, pain, function and health-related QOL data for the Tritanium® Acetabular Shell group will be collected at postoperative time points and compared with the subjects' preoperative status, as well as with the historical control group and with published literature for similar highly porous acetabular shells. It is expected that the HHS, SF-12 and LEAS outcomes in the study group will be comparable to the historical control. It is expected that the EQ-5D outcomes in the study group will be comparable to published results for similar devices.

Lastly, radiographic stability and complications between those implanted with the Tritanium® Acetabular Shell and the historical control group will be reviewed.

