### **Study Synopsis**

Title	A prospective, post-market, multi-center study of the Tritanium® Acetabular Shell
Short Title	Tritanium ® Primary Acetabular Shell Study
Protocol Number	69
Phase	Post-market

	This study will be a prospective, non-randomized evaluation of					
	the Tritanium ® Acetabular Shell for primary total hip					
	replacement (THR) with a cementless application in a					
	consecutive series of patients who meet the eligibility criteria.					
	Half of the cases will use the X3 ® polyethylene insert alone as					
	the bearing surface; the other half will use the MDM™ liner					
	coupled with a compatible ADM/MDM ™ X3 ® insert as the					
	bearing surface. Cases receiving the MDM™ liner may be					
	coupled with Stryker 22.2 mm or 28 mm LFIT ™ CoCr, BIOLOX					
	delta or alumina ceramic heads. All cases will be implanted					
	with a compatible Stryker femoral stem.					
	Data from the Trident® X3® Polyethylene Insert Study will be					
	used as a historical control for secondary objectives. This study					
Methodology	was chosen for the following reasons:					
	Similar indication (primary THR)					
	The acetabular shell (Trident® HA Hemispherical					
	Acetabular Shell) used in this study is a predicate for the					
	Tritanium ® Acetabular Shell, with similar design					
	features.					
	The follow-up intervals and data collected in the Trident®					
	X3 ® Study closely match the design of the current study.					
	The survivorship value used for development of the statistical					
	plan was calculated as a mean of the mid-term results					
	published for three studies of similar acetabular shells. Articles					
	presenting long-term results of additional acetabular shells of					
	similar design will be used for comparison at the end of the					
	study as available.					
	Follow-up of each primary THR case to 10 years					
Study Duration	Enrollment period of 18-24 months					
	Approximate 13-year total duration					
Study Center(s)	7 – 12 centers					
· · · · · · · · · · · · · · · · · · ·	1					

Hypothesis	The success rate, defined as freedom from acetabular revision, for hips implanted with the Tritanium® Acetabular Shell, is no worse than for hips implanted with similar technology as reported in the literature and Trident® X3® Study historical control at 5 years postoperative.					

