	Primary:  To demonstrate, through absence of revision at 5 years postoperative, that acetabular replacement with the Tritanium® Acetabular Shell provides clinical results comparable to similar acetabular components.  Secondary:  • To study rates of screw fixation usage in Tritanium®					
	Acetabular Shell (cluster hole) procedures and compare with those reported in the Trident® X3® Polyethylene Insert Study.					
Objectives	To compare pain, function and health related quality of life (QOL) between the Tritanium® Acetabular Shell combined group and the above-referenced historical control group. The following outcomes measures will be used for this comparison:					
	
 
Harris Hip Score (HHS)
 
Short Form-12 (SF-12)
 
Lower Extremity Activity Scale (LEAS)
 
EQ-5D
 
					
	1-year, 3-year, and 5-year HHS, SF-12 and LEAS data will be compared to the historical control with respect to improvement from preoperative scores. The EQ-5D data will be summarized and presented.					

	An additional Follow-Up Questionnaire will be
	administered annually in postoperative years 6-10 to
	assess patient satisfaction and pain, and to capture
	adverse events. This questionnaire will provide the
	survivorship information necessary to evaluate the
	primary objective of the study.
Objectives	To review radiographic stability and complications
	between those hips implanted with the Tritanium®
	Acetabular Shell and those in the historical control
	group.
	Published complication rates with similar devices, as
	well as complications related to cementless acetabular
	replacement, will be reviewed.
	Cases will be enrolled until 240 cases have received the Tritanium® Acetabular Shell
Number of Subjects	
 
Treatment 1: 120 cases with X3® polyethylene insert
 
Treatment 2: 120 cases with MDM™ liner and ADM/MDM™ X3® insert
 

	Inclusions:
	A. Patient has signed an IRB approved, study specific
	Informed Patient Consent Form.
	B. Patient is a male or non-pregnant female age 18 years
	or older at time of study device implantation.
Diagnosis and Main	C. Patient has primary diagnosis of Non-Inflammatory
Inclusion/Exclusion Criteria	Degenerative Joint Disease (NIDJD).
	D. Patient is a candidate for a primary cementless total hip
	replacement.
	E. Patient is willing and able to comply with postoperative
	scheduled clinical and radiographic evaluations and
	rehabilitation.

	Exclusions:

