#### Statistical Methodology

- A two-sample t-test or Wilcoxon test will be used to compare the HHS, SF-12 and LEAS score at 1-year, 3-year, and 5-year follow-up between the Tritanium® Acetabular Shell and Trident® X3® Polyethylene Insert studies. If there are any statistically significant differences in baseline variables (e.g. age, gender, diagnosis) between the groups, they will be addressed as covariates and ANOVA or ANCOVA will be used.
- EQ-5D health states will be converted to numerical results using the appropriate value set and presented in table format.
- Adverse event (AE) rates will be listed and tabulated, with 95% confidence intervals presented.
- Radiographic data will be summarized in table format.

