infection; two were reported as related to the device; relation to the device in the case of the remaining revision is unknown as the revision was discovered at a site close-out visit and the investigator was no longer at the institution and therefore not available for consultation.

The Trident® Hemispherical Acetabular Shell is one of the earlier Stryker acetabular devices upon which the design of the Tritanium® Acetabular Shell is based. The Exeter® + Crossfire™ US Outcomes Study is a prospective, consecutive series of primary THRs of Exeter® Femoral Stems with Orthinox® Femoral Heads and is a source of clinical data on the performance of the Trident® Hemispherical Acetabular Shell. Subjects participating in this study were implanted with a cemented Exeter® Femoral Stem and an Orthinox® Femoral Head, in combination with a cementless **Trident® Hemispherical Acetabular Shell** (a.k.a. Trident® AD Acetabular Shell, product family 540-01-XXX) and a Crossfire™ polyethylene insert. Enrollment took place at two sites in the United States and is closed with a total of 147 cases. To date, there have been three reported acetabular revisions and one report of acetabular loosening. Two of the acetabular revisions were secondary to infection and one was secondary to recurrent dislocation. Mean follow-up is 4.9 years.

A review of the data collected suggests that the Trident® Tritanium® Acetabular Shell and the Trident® AD Acetabular Shell have performed appropriately for their intended use and present no new risks.

Mid-term clinical and radiographic outcomes have been reported for a competitive product (Trabecular MetalTM Monoblock Acetabular Component System; Zimmer® Inc, Warsaw, IN) of similar design to the subject device.  In a prospective study, 156 primary THAs in 143 patients were followed for a minimum of 8 years (maximum of 10 years). The average HHS improved from 44.0 ± 13.8 (4-86.75) preoperatively to 97.0 ± 6.2 (58.85-100) at the latest follow-up evaluation. Three revisions were reported during the follow-up period; one acetabular component was revised for repeated dislocation and two were revised due to late hematogenous infection. All retrieved components were stable at the time of removal.

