### 9.1.5 Secondary Efficacy Analysis

A two-sided 0.05 alpha level will be used.

For comparison of usage of bone screw fixation between the Tritanium® Primary Acetabular Shell Study and the Trident® X3® Polyethylene Insert Study, a Chi-square test or Fisher's exact test will be used. If there are any statistically significant differences in baseline variables (e.g. age, gender, diagnosis) between the groups, they will be addressed as covariates and ANOVA or ANCOVA will be used.

For comparison of HHS, and SF-12 and LEAS at 1, 3 and 5 years postoperative between the Tritanium® Acetabular Shell and Trident® X3® Polyethylene Insert studies, a t-test or Wilcoxon test will be used. If there are any statistically significant differences in baseline variables (e.g. age, gender, diagnosis) between the groups, they will be addressed as covariates and ANOVA or ANCOVA will be used.

EQ-5D values and changes from baseline will be presented for each interval. Data from the Follow-Up Questionnaire will be used as an input to the Kaplan-Meier survival curve for postoperative years 6-10; any adverse events collected via the Follow-Up

Questionnaire will be reported on a separate Adverse Event eCRF and included in the safety analysis.

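### HHS, SF-12 and LEAS are expected to be comparable to the historical control, but only difference tests are planned, so a non-significant result could be read as comparability that was not shown

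*Combined protocol and SAP*

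**What the plan says.** Section 2.1.2 (Secondary) sets the expectation: "It is expected that the HHS, SF-12 and LEAS outcomes in the study group will be comparable to the historical control". The comparator is the Trident X3 Polyethylene Insert Study, which the synopsis says will be "used as a historical control for secondary objectives". The documents do not give its size, means or standard deviations.

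The analysis in section 9.1.5 is that "a t-test or Wilcoxon test will be used", under the rule "A two-sided 0.05 alpha level will be used". If baseline variables differ significantly between the studies, "they will be addressed as covariates and ANOVA or ANCOVA will be used". The synopsis, under Statistical Methodology, says the same: "A two-sample t-test or Wilcoxon test will be used to compare the HHS, SF-12 and LEAS score at 1-year, 3-year, and 5-year follow-up".

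The synopsis objectives describe a different quantity: "1-year, 3-year, and 5-year HHS, SF-12 and LEAS data will be compared to the historical control with respect to improvement from preoperative scores". So one place compares change from the preoperative score, and the two analysis sections compare scores at the visit.

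No section gives these scores a margin, a confidence interval for the difference between studies, or a power calculation. The plan does use intervals elsewhere. The primary endpoint is judged by the lower bound of a 90% interval against 94% (9.1.4), and adverse event rates carry 95% intervals (9.2.2).

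**The concern.** A t-test, a Wilcoxon test and an ANCOVA significance test all ask whether the two studies differ. None shows that they are alike. A p-value above 0.05 may reflect a small difference or an imprecise estimate, and a p-value below 0.05 may come from a difference too small to matter. Because the plan states an expectation of comparability and offers only the difference test to examine it, a non-significant result is the natural thing to cite in support.

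At stake is the secondary conclusion on pain, function and quality of life, in the 3- and 5-year publications that section 16 anticipates. Without an interval, a reader of those reports cannot see how large a deficit the data leave open.

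**Working it through.** **The plan's own figure.** None exists for these scores. The only sample-size result, 142 cases in 9.4.2, concerns revision. It reproduces: ((1.645·√(0.94·0.06) + 1.645·√(0.99·0.01))/0.05)² = 122.9, and the continuity correction n/4·(1+√(1+2/(n·0.05)))² raises this to 142.2. It has no bearing on HHS, SF-12 or LEAS.

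**Inputs.**
- Study cases: 240 × (1 − 0.20) = 192, from the enrolment target and the 5-year loss rate in 9.4.2. More should be available at 1 and 3 years.
- Control cases: not stated. I assume 200 and show 100 to 300.
- HHS standard deviation: section 1.1 gives the only values, from a study of a competitor's cup: "The average HHS improved from 44.0 ± 13.8 (4-86.75) preoperatively to 97.0 ± 6.2 (58.85-100) at the latest follow-up evaluation". So 6.2 is a follow-up SD and 13.8 a preoperative SD. Neither comes from this trial or its control.
- Alpha: 0.05 two-sided (9.1.5).

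**Formula.** SE = SD·√(1/192 + 1/n_c). For a true difference d, P(p>0.05) = 1 − [Φ(d/SE − 1.96) + Φ(−d/SE − 1.96)].

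**With 200 controls.** √(1/192 + 1/200) = 0.1010.
- SD 6.2: SE = 0.626. For d = 2, d/SE = 3.19 and P(p>0.05) = 10.9%. For d = 3, it is 0.2%.
- SD 13.8: SE = 1.394. For d = 2, d/SE = 1.43 and P(p>0.05) = 70.0%. For d = 3, it is 42.4%.

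**Sensitivity to control size (true 2-point deficit, probability of p>0.05).**

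| Controls | SD 6.2 | SD 13.8 |
|---|---|---|
| 100 | 26% | 78% |
| 200 | 11% | 70% |
| 300 | 6% | 65% |

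**What a result just short of significance leaves open.** The observed difference is then 1.96·SE and the far end of its 95% interval is 3.92·SE. With 200 controls this is 1.2 points reaching 2.5 at SD 6.2, and 2.7 points reaching 5.5 at SD 13.8.

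**Which SD applies.** For visit scores, as in 9.1.5, 6.2 is the closer guide. For change from the preoperative score, as in the synopsis objectives, the SD of change is needed, and it depends on a correlation r that the documents do not give: SD² = 13.8² + 6.2² − 2r·13.8·6.2 = 228.9 − 171.1r. This gives 15.1 at r = 0, 13.8 at r = 0.22 and 12.0 at r = 0.5, so 13.8 is a rough stand-in for that case only. With 200 controls the 2-point figure is 74% at SD 15.1 and 62% at SD 12.0.

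**SF-12 and LEAS.** The documents give no SDs, so no figure can be computed.

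**The case against.** The strongest reply is that the plan never says p>0.05 will be called comparability. The synopsis objective is to compare the scores, and section 2.1.2 states only an expectation, in the same narrative form it uses for EQ-5D, which has no test. Where the sponsor wants a formal claim, it writes a hypothesis and a bound, as in 9.1.3 and 9.1.4. This stands. A reader might infer that the plan commits itself to reading non-significance as comparability, and the documents do not support that. What remains is that they supply no other criterion for the expectation.

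The second reply is that the test is not weak. At SD 6.2, a 3-point HHS deficit is missed in 2.5% of trials or fewer with 100 or more controls. This also stands for visit scores. A reader might take 70% as the general miss rate for a 2-point deficit, but that figure rests on a preoperative SD and is relevant only if change scores are analysed.

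Third, these are unpowered secondary comparisons with a non-randomised historical control, and 9.4.1 already promises descriptive statistics alongside the comparisons. That limits the consequence. Group summaries still do not give an interval for the difference between studies.

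**Conclusion.** The concern holds as a gap between expectation and analysis: comparability is expected, only difference tests are planned, and nothing in the output would show what size of deficit has been excluded. It does not hold as a claim that the plan will misread its p-values, nor as a claim that power is low whatever is analysed.

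The size is uncertain because the plan leaves it so. For a 2-point HHS deficit the chance of p>0.05 is about 11% at SD 6.2 and about 70% at SD 13.8, given 192 evaluable cases and 200 assumed controls. That range comes from inputs the plan does not state and from its not settling whether visit scores or changes are compared. The change is worth making before analysis, although the primary non-inferiority conclusion on revision is untouched.

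**What to change.** In 9.1.5, make the main output for each of HHS, SF-12 and LEAS, at 1, 3 and 5 years, the mean difference (Tritanium minus Trident X3) adjusted for the preoperative score, with its 95% confidence interval. Bring the synopsis objectives, the synopsis methodology and 9.1.5 into line on that quantity.

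Add a sentence that p>0.05 will not be reported as comparability. Without a pre-specified margin, report the interval descriptively and draw no conclusion that the scores are comparable. If the sponsor wants that conclusion, a justified margin for each score has to be set in advance and the interval judged against it.

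The cost is wording plus a change of default model. The plan now starts from an unadjusted t-test or Wilcoxon test and adds covariates only when baseline variables differ significantly; this change makes ANCOVA the default. The Wilcoxon test can stay as a sensitivity analysis. No new data are needed on the Tritanium side. The Trident X3 preoperative scores are needed, but the synopsis comparison of improvement already requires them. The sponsor gives up any comparability claim resting on a p-value alone.

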#### Clinical Outcomes:

Clinical outcomes will be evaluated via the total HHS, including pain, motion and function, preoperatively and at the 6-week, 1, 3, and 5-year visits. Additional HHS data will be obtained at the 7-year and 10-year time points at investigational sites that choose to bring their subjects back in for these optional visits.

#### **Patient Outcomes:**

Pain, function and health related quality of life (QOL) will be compared between the Tritanium® Acetabular Shell combined group, the literature and the above-referenced historical control group. The SF-12 is a 12 item patient self-assessment evaluating health and general wellbeing. The LEAS is a tool that has been developed and validated to evaluate the level of patient activity. The EQ-5D is a standardized instrument for use as a measure of health outcome. These tools will be used to assess patient health-related QOL and will be collected preoperatively at the 6-week, 1, 2, 3, 4 and 5-year visits. Patient outcomes data will also be obtained at the 7-year and 10-year time points at investigational sites that choose to bring their subjects back in for these optional visits, in addition to the required Follow-Up Questionnaire described below.

A Follow-Up Questionnaire will be administered annually in postoperative years 6-10 to assess patient satisfaction and pain, and to capture adverse events. This questionnaire will provide the survivorship information necessary to evaluate the primary objective of the study.

#### Radiographic Outcomes:

To assess radiographic stability as compared with the historical control, radiographs will be taken and collected in the AP pelvis, AP hip and lateral views for the preoperative, 6-week, 1, 3 and 5-year intervals. Additional radiographs will be obtained at the 7-year and 10-year time points at investigational sites that choose to bring their subjects back in for these optional visits.

The AP pelvis and AP hip views allow for observation of any conditions involving the sacral wings, iliac bones, ischium, pubis as well as the femoral head and neck. The lateral view allows for evaluation of the entire hip joint as well as the femoral head, neck and proximal shaft. Suggested radiographic technique for the views required is included in Appendix A.

Radiographs will be evaluated by an independent reviewer throughout the course of the study. Radiographic analysis of the acetabular component will employ three zones (Zone 1 – Zone 3) in the AP views. Numerous parameters will be reviewed by zone, including radiolucency and migration. Radiolucency in at least 50% of a zone and measuring at least 1 mm in width is defined as radiolucency present. Cases that present with migration of greater than 5 mm in any direction or at least 2 mm radiolucency in all zones will be considered radiographic failures.

#### 2.2 Safety

All operative site events as well as all serious adverse events (SAEs), excluding elective procedures, will be collected and compared to the historical control group and to published data. It is expected that the AE rates reported for hips implanted with the Tritanium® Acetabular Shell will be comparable to those reported in the literature for similar porous coated cementless acetabular shells and for the historical control group. Details regarding AE definitions, recording and reporting are in Section 8 of this protocol, Adverse Events.

### 3 Clinical Study Plan

#### 3.1 Study Design

A prospective, post-market, multi-center design will be employed. Radiographs will be assessed by an independent reviewer.

#### 3.2 Number of Centers

Cases will be enrolled at 7 to 12 centers. The enrollment goal ranges from 20 to 34 cases implanted with the Tritanium® Acetabular Shell per center. The enrollment goal range is dependent upon the number of participating centers as well as the relative rates of enrollment of the two treatment groups. Although a range is presented, there is no maximum limit to the number of cases that a center may enroll. In the event that a center far exceeds the overall enrollment goal or enrollment into one of the treatment groups is completed, Stryker may ask the center to cease enrollment so as not to skew the data. All participating centers will comply with the federal regulations regarding patient informed consent and IRB approval. Noncompliance of a study center may result in termination of the center's participation in the study.

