# **9.4.3 Interim Analyses and early Stopping Considerations** No interim analysis is planned.

### 9.4.4 Efficacy Patient Populations

### 9.4.4.1 **Efficacy**

#### Per protocol population:

The study population for analysis will include all subjects who receive the Tritanium® Acetabular Shell. This does not include cases censored from analysis or cases that are unavailable for evaluation at the 5-year primary endpoint.

The primary and secondary efficacy analyses will be based on the per protocol population.

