### Termination Reason Date of Termination

Death Date of death

Investigative center termination Date of study close-out visit

Lost to follow-up Date Stryker termination approval given

Voluntary withdrawal Date subject notified center of withdrawal

Revision/removal of study device Date of revision/removal procedure

Study device not implanted

Surgery not performed

Date of surgery

Date Stryker termination approval given

At the time of study surgery it is required that the following components are implanted:

- Tritanium® Acetabular Shell
- Stryker X3® polyethylene inserts (120 cases)
- Stryker MDMTM liners with ADM/MDMTM X3® polyethylene inserts (120 cases)
- Stryker LFIT™ CoCr heads, BIOLOX *delta* or alumina ceramic heads
- Stryker Universal Adapter Sleeves (for use with BIOLOX delta universal ceramic heads)
- Compatible Stryker femoral stems
- Stryker Orthopaedics Torx Bone Screws

Revision or removal of the Tritanium® Acetabular Shell constitutes a failure and study termination for the subject.

If MDMTM liner, acetabular insert (either X3® or ADM/MDMTM X3®) or femoral head exchange is required during the study, the event is considered a reoperation and does not constitute a failure or study termination.

If femoral stem revision is required during the study, the event is considered a reoperation and does not constitute a failure or study termination.

If the subject fails to return for his/her follow-up appointments, every effort should be made to contact the subject to assess his/her health status. If after attempting to contact the subject through three documented phone calls and a certified letter, the subject still does not respond, he/she will be considered lost to follow-up. A Study Termination eCRF will be completed only after notifying Stryker of the subject's status and being given approval to terminate.

In the event a subject does not have surgery, Stryker should be contacted to discuss if/when the surgery will be rescheduled. If the surgery is rescheduled more than 4 months from the date of preoperative data collection, the subject will need to be re-consented, all preoperative data will need to be re-collected and all original preoperative data will need to be removed from the database. If the surgery is not to be rescheduled or if the subject is no longer considered an

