#### 11.7 Records Retention

It is the investigator's responsibility to retain study essential documents for 2 years after the date of the final report, or in the case of non-compliance, 2 years after the date of investigative center termination. These documents should be retained for a longer period if required by an agreement with Stryker.

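### When a centre is terminated, hips there without a 5-year evaluation drop out of the primary success rate, with no required check of revision status and no rule for revisions already known

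*Combined protocol and SAP*

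**What the plan says.** Section 3.2 states that "Noncompliance of a study center may result in termination of the center's participation in the study". It also says "Cases will be enrolled at 7 to 12 centers", that "The enrollment goal ranges from 20 to 34 cases" per centre, and that "there is no maximum limit to the number of cases that a center may enroll".

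Section 10.3 lists reasons for which subjects may be withdrawn and the date to enter for each. One entry reads "Investigative center termination Date of study close-out visit". The draft Study Termination eCRF in Appendix E has a matching box. It asks whether the device was in place at the last contact, not whether it is in place at closure.

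Section 9.4.4.1 bases the primary analysis on a per-protocol population that leaves out "cases that are unavailable for evaluation at the 5-year primary endpoint". Section 9.3 rules out imputation. Section 9.1.4 defines success as no shell revision or removal within 5 years and compares the lower 90% limit with 94%, without naming the interval method. The Kaplan-Meier curve is shown in addition. Section 9.4.4.3 puts every enrolled subject who received the shell into that survival analysis.

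No section provides for transfer of follow-up to another centre, follow-up run by the sponsor, or a check of each hip's present status at close-out.

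Section 11.7 has centres keep records for 2 years after the final report but, "in the case of non-compliance, 2 years after the date of investigative center termination", with longer retention if an agreement with the sponsor requires it.

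**The concern.** Read together, sections 3.2, 10.3, 9.4.4.1 and 9.3 let a decision about a centre determine which hips enter the primary success rate. The shells stay in the patients, and whether they have been revised could still be learned. Section 7.4 already uses a questionnaire, completed by telephone or at home, that asks about surgery on the study hip.

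This differs from ordinary drop-out in two ways. It removes a block of hips at once, and the reason may be connected with how well the centre reports events. Section 1.1 gives an example from the study of the revision shell: for one of its nine reported revisions, "the revision was discovered at a site close-out visit". A shell revision can therefore go unreported until someone looks.

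At stake is the 5-year success rate itself, in a test decided by a handful of revisions. The 20% loss allowance in section 9.4.2 protects the number of evaluable hips. It does not protect against bias in which hips are evaluable.

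**Working it through.** **1. The plan's sample size.** Inputs from sections 9.4.2 and 9.1.4: success 99% against a limit of 94%, one-sided 5% (lower end of a 90% interval), 95% power.

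- n = [(1.645·√(0.94·0.06) + 1.645·√(0.99·0.01)) / 0.05]² = 122.9
- With continuity correction, (n/4)·[1 + √(1 + 2/(n·0.05))]² = 142.2, which matches the stated 142.
- 142/0.80 = 177.5, against the stated 177.

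**2. Share of one centre at the enrolment goal.** 240/12 = 20 and 240/7 = 34.3. 20/240 = 8.3% and 34/240 = 14.2%. There is no cap, so a centre may be larger. It may also close before reaching its goal, and hips already seen at 5 years are not excluded. The range is a guide, not a bound.

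**3. Power after losing one centre.** With 20% loss, 240 × 0.8 = 192 hips are evaluable.

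- 20% loss also applied within the closed centre: 20 × 0.8 = 16 or 34 × 0.8 ≈ 27 leave, so 176 or 165 remain.
- The whole centre taken from the 192: 172 or 158 remain.

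All exceed 142. Exact power at a true 99% is about 97 to 99%.

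**4. Direction of the bias.** Assumed for illustration: 192 evaluable hips, six revisions, and a closed centre with 16 evaluable hips, one of them revised. Exact (Clopper-Pearson) lower limits, 5% in the tail:

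| Handling of the closed centre | Revisions / hips | Lower limit | Against 94% |
|---|---|---|---|
| Centre not closed | 6/192 | 93.93% | fails |
| Revision not seen or dropped; all 16 hips leave | 5/176 | 94.12% | passes |
| Revision kept; 15 unrevised hips leave | 6/177 | 93.42% | fails, further below |

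The same closure moves the limit up or down depending on a rule that the plan does not state.

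**5. How fragile the reversal is.**

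- Interval method: for 6/192 the Wilson lower limit is 94.07% and the Wald limit 94.81%. Both already pass, so neither gives a reversal in the device's favour.
- Starting count: 5/192 passes on exact limits (94.60%), so nothing is left to reverse. From 7/192 (93.26%, fails), a closed centre with 27 evaluable hips must hold three of the seven: 4/165 gives 94.54% and passes, while 5/165 gives 93.73% and fails.
- Centre size: from six revisions, a centre with 27 evaluable hips must hold two of them (4/165). If revisions fall at random over the 192 hips, the chance of two or more there is about 20%.
- Likelihood: at a true 99%, six or more revisions in 192 has probability 1 − 0.9866 = 1.3%.

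**6. Records.** Section 3.4 allows up to 24 months of enrolment, and the Evaluation Schedule gives the 5-year visit a window of 4 months. The last window closes at about month 24 + 60 + 4 = 88. A centre terminated before about month 88 − 24 = 64 could discard its source documents before then, unless an agreement says otherwise.

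**The case against.** The strongest reply is that revisions do not disappear with a centre. Section 10.3 makes a shell revision a failure with its own termination date, and section 9.1.4 defines success by revision within 5 years. Section 8.3 requires notice to the sponsor within 24 hours, and section 6.2 sends explants for retrieval. A revision before closure should therefore already be in the sponsor's data. This stands. A reader might infer that closure takes out every hip at the centre together with its revisions. The documents do not support that: hips already seen at 5 years stay in, the wording in sections 3.2 and 10.3 is permissive, and a known revision is a defined failure. What remains open is whether section 9.4.4.1 treats a hip revised before closure as unavailable at 5 years.

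A reader might also infer that closing one centre would turn a failed study into a success. Step 5 shows that this needs particular counts, exact limits and a revision total that is improbable under the planned 99%.

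Nor do the documents show that non-compliant centres hide revisions. The sentence before the termination rule in section 3.2 concerns consent and IRB approval. In the earlier study the late revision was found at close-out and counted; what stayed unknown was its relation to the device. That is irrelevant here, because this endpoint is revision for any reason. The example shows only that a check at close-out can find something.

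The survival analysis keeps all implanted hips, which helps, but section 9.1.4 does not let it decide the 94% comparison. The records point is minor: data are held in the sponsor's system (section 11.1), source documents for serious events are uploaded (section 8.3), and monitoring takes place at least yearly (section 13.1). Discarding site records later does not remove data from the analysis.

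**Conclusion.** The point holds as a gap in the primary analysis that takes effect only if a centre is terminated. Unrevised hips there without a 5-year evaluation then leave the primary success rate, no current revision status is required, and the handling of revisions known before closure is undefined. At the enrolment goal 8 to 14% of the cohort is exposed, more or less depending on the centre's size and how many of its hips have passed 5 years.

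The direction is not fixed. Revisions unreported before closure or occurring after it favour the device when missed. Known revisions kept while unrevised hips leave count against it, by about half a percentage point in the lower limit in the example (93.93% to 93.42%). The counts in that example are assumed. Power is adequate in every case examined, so the issue is bias and an unstated rule, not sample size.

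**What to change.** **Section 10.3.** At any centre's close-out visit, require a chart and telephone check of current revision status, with date, for every implanted hip. Where consent and IRB approval allow, continue the existing telephone or mail questionnaire for those hips to 5 years. This second step is desirable but optional.

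**Sections 9.1.4 and 9.4.4.1.** State that any known shell revision within 5 years counts as a failure whether or not the centre has closed. Keep revision-free hips in a 5-year Kaplan-Meier estimate in all implanted hips, censored at the date last known in place. Base the 94% comparison on that estimate or check it against it, and name the interval method. Censoring assumes that closure is unrelated to revision, which is why the status check is needed as well. The documents do not say whether the 5-year analysis has been run. If it has, report the Kaplan-Meier comparison as a sensitivity analysis.

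**Section 11.7.** As a minor alignment, have terminated centres keep records until 2 years after the final report, as other centres do.

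**Cost.** A short amendment, possibly consent and IRB wording for continued contact, and one status check per hip at a closed centre. No new patients or procedures are needed.
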